## **Background and Rationale**

The Marshallese population suffers from a significant and disproportionate burden of type 2 diabetes. The rate of type 2 diabetes among the Marshallese is one of the highest of any population group in the world—at least 400% higher than the general US population. Our systematic review of local, national, and international data found estimates of diabetes in the Marshallese (populations living both in the US and Marshall Islands) ranging from 30% to 50% compared to 8.3% for the US population and 4% worldwide. Causes for this disparity have not been completely unraveled and are partially embedded in the history of the Marshall Islands. Between 1946 and 1958, the US military tested nuclear weapons on several of the Marshall Islands. People who inhabited the bombed islands and atolls were relocated, but Marshallese living on nearby atolls that were not evacuated experienced nuclear fallout during and after nuclear tests. Because of the nuclear testing, the Atomic Energy Commission lists the Marshall Islands as one of the most contaminated places in the world, and several studies demonstrate ongoing health effects from the nuclear testing. The nuclear contamination resulted in significant and long-term changes in diet and lifestyle of the Marshallese. These changes in diet and lifestyle have contributed to an increased rate of type 2 diabetes. The Compact of Free Association between the Republic of the Marshall Islands (RMI) and the US, signed in 1986, permits the US to conduct military activities in the Marshall Islands and also allows Marshallese individuals to come to the US without a visa. The Marshallese population living in the US tripled between 2000 and 2010, with Arkansas having the largest population of Marshallese living outside of the RMI.

Diabetes self-management education (DSME) is an evidence-based model that has been shown to improve glycemic control, reduce diabetic complications, and reduce the cost of managing diabetes. Traditional implementation approaches of DSME have not been effective in Marshallese populations, indicating that a unique approach tailored to this population is needed. Because of the disproportionate burden of diabetes and related complications experienced by this high-risk population, a novel adaptation of the evidence-based DSME model and subsequent testing in a community-based setting are needed.

Using a CBPR approach, we have conducted four focus groups and individual interviews with the Marshallese community to better understand how to best address the well-established need for diabetes education. Through interviews and focus groups, Marshallese participants pointed out that the delivery method and the concept of self-management as an individual experience are problematic components. DSME was designed with a very Western societal approach, which is highly individualistic. The Marshallese have a highly collectivist culture and the idea of self-management is counter to their cultural values. As stakeholders described, we eat together from one pot. For one person to refuse the food from that one pot is not just inconvenient, it is shameful. It shames the person and the person's family. It is not an acceptable option. We will not do it. The interviewees stated that any changes must be a family change. Incorporating

Title: *Family Model of DSME in the Marshallese Community*

PI: *[name]*

collectivist and family concepts into the delivery mechanism is imperative. Through the interviews and focus groups, the Marshallese community suggested that DSME be implemented within a family model with a family group receiving DSME so that the entire family can benefit and the patient can be supported in their effort to make lifestyle changes. Because ~30-50% of the Marshallese community have type 2 diabetes, this approach could be even more beneficial.

### **Hypothesis and/or Specific Aims or Objectives**

We hypothesize that a culturally adapted DSME implemented in a family model will result in better diabetes management outcomes compared to traditional DSME for the Marshallese.

In the family delivery model, a participant is encouraged to invite his/her family members to the diabetes educational sessions. As outlined by stakeholders, the model has several potential benefits. First, patients are empowered to invite the people they define as family and as appropriate for taking part in the sessions with them. Second, the education will engage the patient-defined support unit. Third, given the high rate of diabetes within the community, it is highly probable that others within the group will have Type 2 diabetes or pre-diabetes and may benefit from the intervention as well.

Our aim is to test a Family Model of DSME using a mixed-methods approach. Marshallese participants with type 2 diabetes will be recruited. Those who are assigned to the family model will be asked to invite one to ten adult members of their families to participate in the DSME. Given that ~30-50% of adults in the Marshallese community have type 2 diabetes, and the Marshallese typically have large families, recruitment for this nontraditional model is plausible. Furthermore, the method was designed from input from our CBPR partnership with the Marshallese.

This research is highly translational. It will help bridge the gap between knowledge of an effective DSME intervention and actual implementation of the intervention among a Pacific Islander population with especially high rates of type 2 diabetes and significant health disparities.

### **Study Design and Procedures**

We will conduct a comparative effectiveness evaluation using a randomized control trial design of the adapted Family Model of DSME, and compare results of the Family Model of DSME with traditional DSME within the Marshallese population. The family model will cover the same concepts as the traditional format. However, the family model will incorporate culturally-adapted education and recommendations aimed at engaging family members in the management of the primary participant's diabetes, and family members will be invited to fully participate in the study. By contrast, the traditional model provides diabetes self- management education to the diabetic participant only, and the participant's family members do not participate in the classes or any other part of the

Title: *Family Model of DSME in the Marshallese Community*

PI: *[name]*

study. Biometric and survey data will be collected pre-intervention, post-intervention, 6 months post-intervention, and 12 months post-intervention. In the event missing data is identified, participants will be contacted to collect the missing data. A qualitative debriefing session will be held for each family between the final DSME session and the 6 month post-intervention to obtain qualitative data regarding the participant's perceptions of the intervention and implementation process. Participants will be offered a \$20 gift card as compensation for their time for each biometric data collection event and the qualitative debriefing session.

**Randomized participant assignment.** Six cohorts will be recruited, approximately three months apart. Each cohort will be comprised of 75 participants with diabetes, with 50% being assigned to the Family Model arm and 50% being assigned to the traditional DSME control group. The study sample size will be the total of each cohort; thus a total of 300 diabetics and up to 2000 family members (only those in the family model arm will be inviting family members). We initially chose an unequal group design (70/30), but after assessing Cycle 1 attrition, we needed to adjust the ratio in order to have sufficient control group numbers for analysis. Discussion with stakeholders resulted in support for this modification. Each participant will be randomly assigned to a group after consent.

Randomization will occur at the family level rather than the individual level. Prior to randomization, consented participants will be grouped according to family unit to prevent two diabetics in the same family being randomly assigned to different groups, creating cross-contamination. Once an entire cohort is recruited and assigned a family identification number, each number (family) will be randomly assigned to a study arm. Randomization will be conducted utilizing the Excel random number generation function. Randomization will be conducted by an investigator who will have no interactions with potential participants and has no supervisory role with program staff responsible for recruitment consent, or intervention delivery. Designated study staff will send the investigator a list of consented participants prior to the start of each new DSME cycle. The investigator will deliver the study arm assignments to a designated study staff member at the project site. Participants will be notified of their group assignment at least one week prior to commencement of study activities.

**Study arms description.** The standard care group will receive traditional DSME in a group format. However, those in the standard group will attend classes with other unrelated participants, unless two or more diabetics within the same family get assigned to the control group. The intervention group will receive the adapted Family Model of DSME in a family format, as described above. Participants in the Family Model will be encouraged to invite one to ten family members to participate in the DSME sessions as well as all other study events.

**Intervention:** Both the Family Model and the traditional DSME will include 10 hours of content comprised of 8 modules. The classes will be delivered over a 6-10 week period and each class will be approximately 75 minutes in length. To ensure fidelity, the DSME programs in both study groups will be facilitated by a Certified Diabetes Educator (CDE) or other licensed healthcare professional with expertise in the content areas. A translator/interpreter fluent in both English and Marshallese will be present for every

Title: *Family Model of DSME in the Marshallese Community*

PI: *[name]*

session. The family model intervention will be co-facilitated by a Certified Diabetes Educator or other licensed healthcare professional and a Marshallese staff person fluent in both English and Marshallese. The core elements of DSME intervention are: healthy eating, being active, monitoring, understanding blood glucose and taking medication, problem solving, reducing risks and healthy coping, mitigating complications of diabetes, and goal setting. These core elements will be maintained across both groups and are consistent with the American Association of Diabetes Educators' AADE seven self-care behaviors. Sessions will be provided at the Springdale AHEC clinic, the Jones Center, or at a location of the participant's choice.

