### Study Population

**Recruitment and Consent:** There are ~11,000 Marshallese living in Springdale, Arkansas. Using conservative estimates, 3,000 of the Marshallese living in Springdale, Arkansas have type 2 diabetes, providing a sufficient participant pool for recruitment. Participants will be recruited through the three primary clinics that care for the Marshallese—the Community Clinic (a Federally Qualified Health Center), the Springdale Family Medical Center, and the [name] Clinic in Springdale. In addition, participants will be recruited through local Marshallese churches, community leaders, and Yokwe.net, the primary social media site for the Marshallese community. A more detailed recruitment plan is outlined in the following section. Potential participants will be provided information about the study and given the opportunity to take a brief eligibility screener that determines and documents study eligibility. Up to 300 participants with diabetes (initial participants) will be recruited and enrolled, and each participant in the

Title: *Family Model of DSME in the Marshallese Community*

PI: *[name]*

treatment group will be asked to invite between one and ten family members to attend the diabetes education sessions and potentially join the study. All members of the research team will be trained and certified in participant consent procedures, the study protocol, human subjects protection, and HIPAA regulations. During the presentation/discussion of the study, potential participants will be screened for eligibility. Inclusion/exclusion criteria are as follows:

Initial Participant Inclusion Criteria

- 18 years and older
- Self-reported Marshallese ethnicity or descent
- Self-reported Diabetes Mellitus Type 2 diagnosis by a health care provider

Initial Participant Exclusion Criteria

- Younger than 18 years of age
- Not Marshallese ethnicity or descent
- No reported Diabetes Mellitus Type 2 diagnosis

Family Member Inclusion Criteria

- 18 years and older

Family Member Exclusion Criteria

- Younger than 18 years of age

Potential participants who are interested in joining the study will be provided the opportunity to ask questions, consent and enroll in the study. At enrollment, a participant contact information form will be completed and include participant contact information (phone numbers, address, e-mail), preferred method of contact (i.e. text, phone, mail, e-mail), and demographic information.

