## **Data Analysis**

### Sample size and power considerations

All of the power and sample size calculations and estimations were performed using PASS 2008 (NCSS, LLC. Kaysville, Utah. [www.ncss.com](http://www.ncss.com)). Our study design is a randomized two-group construct with 4 repeated time points (baseline, post intervention, 6 months, and 12 months). So at its core, the study is a two-factor design with repeated measures, which can be expanded into a general linear regression model, with main covariates being group assignment, time, their interaction, and adjustment for other covariates. The sample sizes will achieve 80% power to detect a medium effect of 0.3 in a design with 4 repeated measurements having a compound symmetry covariance structure. The correlation between observations on the same subject is assumed to be of moderate magnitude at 0.5, and the alpha level is 0.05. This hypothesized detectable effect is of the same magnitude as a study that reported approximately 0.5% change in HbA1c with the standard deviation of the change being 1.5%.

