#### Analysis of primary outcome

The primary outcome is change in HbA1c between baseline, post intervention, 6 months post-intervention, and 12 months post-intervention. Repeated measures of these outcomes will be obtained at four visits as described. Our primary analytic approach will use general linear models (GLM) and mixed models for continuous repeated measures to model the mean outcome differences and covariance structures between the groups. Using these models, group effects will be estimated and tested by comparing group-specific means at post intervention, 6 months, and 12 months, while conservatively adjusting for the baseline differences in ANCOVA like mixed regression models.

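### Six cohorts of 75 make 450 participants with diabetes, but the protocol gives their total as 300; the total should be reconciled and the power restated at it

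*Combined protocol and SAP*

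**What the plan says.** The paragraph on randomized assignment in Study Design and Procedures gives the schedule: "Six cohorts will be recruited, approximately three months apart". It continues: "Each cohort will be comprised of 75 participants with diabetes, with 50% being assigned to the Family Model arm". The total follows directly: "The study sample size will be the total of each cohort; thus a total of 300 diabetics". The same paragraph records a change of allocation: "We initially chose an unequal group design (70/30), but after assessing Cycle 1 attrition, we needed to adjust the ratio". The 50/50 split is therefore current text.

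Study Population, under Recruitment and Consent, repeats the total as a ceiling: "Up to 300 participants with diabetes (initial participants) will be recruited and enrolled".

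Sample size and power considerations gives no number of participants. It says: "The sample sizes will achieve 80% power to detect a medium effect of 0.3 in a design with 4 repeated measurements", with compound symmetry, a within-subject correlation of 0.5 and alpha 0.05. It describes the effect as of the same magnitude as a cited study's "approximately 0.5% change in HbA1c with the standard deviation of the change being 1.5" percent.

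Analysis of primary outcome tests group effects by "comparing group-specific means at post intervention, 6 months, and 12 months, while conservatively adjusting for the baseline differences". It does not say whether the target is each visit or an average over visits.

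Three other features bear on the effective sample size. Families, not individuals, are randomized (Study Design and Procedures). Primary participants whose initial HbA1c is below 6.5 are unenrolled as primary participants (Participants and family member measures). Attrition in Cycle 1 was enough to prompt the change of ratio.

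**The concern.** The total is presented as the sum of the cohorts, and it is not that sum. Staff cannot both run six intakes of 75 and stop at 300. A reader cannot tell whether recruitment ends after four intakes or six.

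The power statement refers only to unnumbered sample sizes, so it depends on the figure in dispute. It does not name the comparison that the 80% covers. It also shows no allowance for attrition, for unenrolment after the HbA1c check, or for two or more primary participants sharing a family. How much room 300 leaves therefore cannot be read from the plan and has to be worked out under assumptions.

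**Working it through.** **1. The plan's own total.** Inputs: six cohorts and 75 per cohort (Study Design and Procedures).

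- 6 × 75 = 450. The stated 300 is not reproduced; the gap is 450 − 300 = 150.
- 300 would need 300 / 75 = 4 cohorts of 75, or 300 / 6 = 50 per cohort.
- If each cohort fills, 4 × 75 = 300 is reached at the fourth intake. The remaining 2 × 75 = 150 lie above the ceiling.

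**2. Which figure is likelier to be wrong.** The 300 appears in two sections. Table 2, Year 1, has 53 intervention and 22 control participants, and 53 + 22 = 75, one full cohort. That supports the cohort size and points to the cohort count. It is an indication, not proof.

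**3. Power at 300 for the planned analysis.** From the power section: effect 0.3, correlation ρ = 0.5, alpha 0.05. Assumed: 0.3 is a standardized mean difference, the test is two-sided, and the arms are 150:150.

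With baseline as covariate under compound symmetry, the variance factors v are:

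- one post-baseline visit: v = 1 − ρ² = 1 − 0.25 = 0.75
- mean of three post-baseline visits: v = (1 + 2ρ)/3 − ρ² = 0.667 − 0.25 = 0.417

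SE = √[v × DE × (1/n₁ + 1/n₂)], where DE is the family design effect. Power is from the noncentral t with noncentrality 0.3/SE. At 150:150 and DE = 1:

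- one visit: SE = √(0.75 × 2/150) = 0.100, noncentrality 3.00, power 84.9%
- mean of three: SE = √(0.417 × 2/150) = 0.0745, noncentrality 4.02, power 98.0%

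| Scenario | One visit | Mean of three visits |
|---|---|---|
| 150:150, DE 1.0 | 84.9% | 98.0% |
| 135:135 (assumed 10% loss), DE 1.0 | 80.9% | 96.7% |
| 150:150, DE 1.1 (assumed) | 81.4% | 96.9% |
| 135:135, DE 1.1 (both assumed) | 77.2% | 95.2% |
| Total needed for 80%, DE 1.0 | 264 | 148 |
| Loss tolerated from 300, DE 1.0 | about 12% | about 51% |

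The last row follows from the totals: 1 − 264/300 = 12% and 1 − 148/300 = 51%.

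**4. Allocation.** If Cycle 1 randomized 75 at 70/30 and the other 225 were split equally, the arms would be about 165:135. Power is then 84.5% and 97.9%, so the mixed ratio changes little.

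**The case against.** The strongest reply is that the working total is clear. Enrolment is capped at 300 in its own section, the cohort wording is a slip, and the planned analysis has adequate power at 300. Much of this stands. The cap does make 300 the likelier intended figure, and both baseline-adjusted comparisons exceed 80% before loss and clustering. The fourth-intake problem also assumes that every cohort fills. The cap does not remove the contradiction, because the same paragraph still derives 300 from inputs that give 450.

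A reader might go further and infer that 300 leaves no room for loss. An unadjusted single-visit comparison at effect 0.3 has only 73.6% power, and an unadjusted change score at 0.5/1.5 = 0.333 has 82.1%, tolerating about 5% loss. The documents do not support that inference, because Analysis of primary outcome plans baseline adjustment and neither of these tests has it.

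A reader might also see two competing effect sizes, 0.3 and 0.333. The power section uses one design effect, 0.3, and cites the other study only as being of the same magnitude.

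Family clustering may be small. The primary analysis concerns participants with diabetes, so it arises only where several of them share a family. The documents give no such count and no intraclass correlation.

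Table 2's completers (75 + 110 + 50 = 235) might be read as a built-in allowance for loss. The power section does not refer to them, and the Year 1 figure is a full cohort, so that reading is not supported either.

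**Conclusion.** The contradiction between 450 and 300 is certain and rests on no assumption. The documents do not establish that 450 is right. The cap of 300 makes the cohort count or size the likelier error, and Table 2 favours the count.

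The power question is secondary. A shortfall at 300 is not shown. If the 80% refers to the mean over visits, the margin is wide. If it refers to a single visit, the margin is thin: either assumed allowance alone leaves power just above 80%, and the two together take it below. These results depend on reading 0.3 as a standardized mean difference, a two-sided test, equal arms and the stated correlation of 0.5. The 10% loss and the design effect of 1.1 are illustrations, since the plan gives neither. The point should be fixed, mainly because a basic planning figure contradicts its own inputs.

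**What to change.** 1. State one total with a cohort count and size that multiply to it: for example four cohorts of 75, or six of 50 if the cohort size is the error. Use it in both Study Design and Procedures and Study Population.
2. Restate power, or the detectable effect, at that total for the baseline-adjusted comparison in Analysis of primary outcome. Name the contrast: each visit, or the average over visits.
3. Show the assumed loss, covering both attrition and unenrolment for HbA1c below 6.5, and the assumed family design effect.

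The cost is protocol wording and one recalculation. The downside is that the stated power or detectable effect may become slightly less favourable.

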#### **Survey Data**

We have developed a survey instrument that includes modules from the Diabetes Care Profile (DCP), the Behavioral Risk Factor Surveillance Survey (BRFSS), and internally developed modules pertaining to diet and physical activity. We will also collect demographics, contact information, and a medication inventory using study specific forms. The documents will be translated into Marshallese and field tested by the study's Marshallese Community Advisory Board. These surveys/forms will be administered at the pre-intervention data collection events and all post- intervention data collection events. All surveys will be either self-administered or interviewer-administered, depending on the preference and/or literacy of the participant. A Marshallese translator/interpreter will be present for all DSME sessions and data collection events.

Title: *Family Model of DSME in the Marshallese Community*

PI: *[name]*

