**Participants and family member measures.** As discussed above, the participants assigned to the treatment group will be asked to invite between one and ten family members to join them for the education sessions. Family members may or may not have Type 2 diabetes. Family members will be provided the opportunity to consent after the initial participants have invited them to take part in the study. Primary analysis will be based on the participants with diabetes. In addition, we will collect and analyze the outcomes of the family participants who have consented and report any value added by including outcomes of family members. We will collect biometric and survey instrument data on family members who consent and participate. If family members are found to have elevated HbA1c during the data collection but have not previously been diagnosed with diabetes, we will refer them to a health care provider.

Primary participant's diabetes status will be confirmed by their HbA1c at the time of initial data collection. Primary participants who do not have HbA1c results indicative of diabetes, 6.5 or above, will be unenrolled from the study as primary participants. If they were randomized into the family arm of the study and another family member does have HbA1c results indicative of diabetes, participation of the entire family unit (including with an HbA1c less than 6.5) will continue.

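### Baseline data appear to be collected after families are randomised, and probably after participants learn their arm

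*Combined protocol and SAP*

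**What the plan says.** The combined protocol and SAP does not set out consent, baseline, randomisation and notification as one sequence. The order has to be pieced together.

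- **Study Design and Procedures, on randomisation:** "Each participant will be randomly assigned to a group after consent". The trigger is recruitment: "Once an entire cohort is recruited and assigned a family identification number, each number (family) will be randomly assigned to a study arm". The randomising investigator works from a list of people who have consented, sent before each cycle begins. Completed baseline measurement is not a condition.
- **Same section, on notification:** "Participants will be notified of their group assignment at least one week prior to commencement of study activities".
- **Same section, on data collection:** "Biometric and survey data will be collected pre-intervention, post-intervention, 6 months post-intervention, and 12 months post-intervention". Survey Data agrees: "These surveys/forms will be administered at the pre-intervention data collection events". Table 1 puts the medication inventory at every data collection event.
- **Study Population, on participant and family member measures:** "Primary participant's diabetes status will be confirmed by their HbA1c at the time of initial data collection". Primary participants below 6.5 are removed from that role. An exception, which opens "If they were randomized into the family arm of the study", keeps the whole family in the study when another member meets the threshold.

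The baseline values are then used twice. The primary and secondary outcome sections adjust for baseline in ANCOVA-type mixed models. The Missing data section promises to analyse everyone randomised, with multiple imputation by PROC MI.

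**The concern.** In an open trial, a baseline taken once the arm is known is no longer guaranteed to be independent of the arm. Two consequences matter here.

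**Missing baselines.** A participant who leaves on learning the assignment, before the first data collection, is randomised but has no HbA1c, biometric or survey value. The intention-to-treat analysis must still include that person. Only the contact and demographic information taken at enrolment is available to impute from. Nor can leavers be compared with stayers on HbA1c, so selective departure would go unseen.

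**Influenced self-report.** The survey has modules on support, understanding and health behaviour. A person who has just been asked to bring up to ten relatives may answer the support items differently from a person assigned to attend alone. Adjusting for such a baseline carries part of that difference into the estimated effect.

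**Working it through.** **Step 1: the order of events.** The plan states no figure to reproduce, so this step rests on the text.

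| Question | What the sections support |
|---|---|
| What triggers randomisation? | Consent, a fully recruited cohort and family numbers; no baseline measurement is required |
| Does baseline HbA1c follow randomisation? | Yes, by implication: the rule acting on the initial HbA1c provides for people already randomised |
| Do surveys and the medication inventory follow it too? | Yes, by implication: they belong to the same pre-intervention events |
| Does baseline follow notification? | Probable, not stated |

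Three things point towards notification first. Relatives consent only after being invited, which happens only in the Family arm. They are invited to all study events, not just classes. Table 2 groups recruitment with random assignment, and data collection with the intervention sessions. None of these is conclusive.

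**Step 2: size of a reporting shift.** Inputs:

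- Within-person correlation 0.5 (Sample size and power considerations).
- Equal variances at each visit, as compound symmetry implies. The ANCOVA slope is then 0.5 × (SD / SD) = 0.5.
- A uniform shift *s* in the Family arm's self-reported answers. The documents give no value, so 0.1, 0.2 and 0.3 SD are assumed.

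Estimates:

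- Adjusted difference = follow-up difference − 0.5 × baseline difference
- Change-score difference = follow-up difference − baseline difference

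If the shift is present at baseline only, the biases are −0.5*s* and −*s*:

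| *s* (SD, assumed) | Adjusted difference | Change score |
|---|---|---|
| 0.1 | −0.05 | −0.10 |
| 0.2 | −0.10 | −0.20 |
| 0.3 | −0.15 | −0.30 |

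The sign follows the shift. Family-arm answers inflated at baseline reduce the estimated gain; deflated answers increase it.

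**Step 3: if the shift persists.** Participants also know their arm at follow-up. If the same shift is present at both times, the change-score bias is *s* − *s* = 0 and the adjusted bias is *s* − 0.5*s* = +0.5*s*. For *s* = 0.2 that is 0 and +0.10 SD. With a baseline taken before randomisation, the same follow-up shift would leave the full +0.20 SD in either estimate. The table in Step 2 therefore holds only for a shift confined to baseline.

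**Step 4: missing baselines.** The documents do not say how many people leave between notification and baseline. Cycle 1 attrition was large enough to change the allocation from 70/30 to protect control numbers, but its timing is not reported. No figure can be put on this part.

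**The case against.** The strongest reply is that no sentence puts baseline after notification. The notification sentence could refer to classes alone, in which case baseline might fall between randomisation and notification. The exception for families with another eligible member does not prove that relatives had already been invited, since the plan expects some families to have two consented members with diabetes before randomisation. This stands: the notification order is an inference. It does not remove the implied order of randomisation and baseline, and nothing in the plan requires baseline to come before notification.

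The bias figures can also be challenged. The shifts are assumptions, and Step 3 shows how far the result depends on their being confined to baseline. A reader might set 0.10 SD against the 0.3 effect in the power section and infer that a third of the target is at risk. The documents do not support that: the 0.3 is justified by an HbA1c change of 0.5 with SD 1.5, whereas the shift concerns survey answers, for which the plan sets no target.

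HbA1c, weight, glucose and blood pressure are measured by trained staff under standardised procedures. There is no clear mechanism by which learning the arm shortly beforehand would move them much. The plan also says that participants with missing data will be contacted, but a value obtained after classes begin cannot serve as a baseline.

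**Conclusion.** The concern holds in a limited form. The plan implies that primary participants' baseline data are collected after randomisation. That they are collected after notification is likely but unstated. The firmer consequence is that someone can be randomised and leave with no baseline for the adjusted models or the imputation; how often cannot be told from the documents. The second is possible influence on self-reported baselines: 0.05 to 0.15 SD in an adjusted difference for assumed shifts of 0.1 to 0.3 SD, and the full shift in a change score, on condition that the shift is confined to baseline, the correlation is 0.5 and variances are equal.

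A reader might infer that the primary HbA1c comparison is seriously biased by this ordering. The documents do not support that: the direct effect on HbA1c and the other objective measures should be small. Nor would re-ordering cure reporting bias at follow-up. The change is worth making because it is cheap and secures a baseline, free of knowledge of arm, for participants before they are randomised.

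**What to change.** For every cohort not yet randomised, revise the randomisation text in Study Design and Procedures and the participant and family member measures in Study Population to give one explicit order:

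1. Consent the cohort.
2. Hold the full baseline event for primary participants: HbA1c, other biometrics, surveys and medication inventory.
3. Randomise families.
4. Release the assignments.
5. In the Family arm, collect relatives' baseline data before classes start.

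Define the activities that notification must precede. Reconcile the exception for people already randomised to the Family arm with the new order, since the HbA1c check would then come before randomisation.

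For cohorts already randomised (at least one, since Cycle 1 attrition has been assessed), report notification and baseline dates and baseline completion by arm.

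The cost is modest. Cohorts are already randomised as a block after recruitment, so this moves an existing visit and adds none for primary participants. There are two downsides. Relatives' baseline is taken at a separate time from the primary participant's. Baseline timing will also differ between earlier and later cohorts, and the allocation ratio has changed across cohorts too, so the models should adjust for cohort.
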